## 1.0 Protocol Summary

Study Purpose	The purpose of this pilot study is to evaluate the acceptability of an artificial intelligence powered mental health support tool for mental health wellness amongst physicians in training.
Research Procedures	The primary research procedures are:
	• The primary research procedure will be the utilization of artificial intelligence powered mental health support session through a web browser for physicians in training to address symptoms related to depression and anxiety. A pre and post intervention survey, evaluating depression symptoms with the standardized PHQ-9 questionnaire and anxiety symptoms with the standardized GAD-7 questionnaire will be conducted to assess changes in mental health wellness.
Subject Population	The study will enroll physicians in training, including Internal Medicine residents and Gastroenterology fellows.
Duration of Subject's Participation	
 
The study includes at least 4 sessions.
 
The total study duration for each subject is 3 months.
 

## 2.0 Background, Rationale

Mental health is an important aspect of trainee's wellbeing, training and success. Mental health concerns may arise as changes in behavior and emotions and include symptoms related to stress, anxiety and depression (Nobleza, 2021). Physicians are an at-risk profession for suicide, and a recent systemic review and meta-analysis found that physicians in the USA are at higher risk for suicide as compared to other countries [Dutheil, 2019]. Depression is a known risk for suicide, with an estimated 20-43% of trainee physicians experiencing depression and symptoms of depression [Mata, 2015]. Psychosocial works factors thought to contribute to depression include lack of a cohesive teamwork, social support, delivering bad news, frequent contact with illness and death [Dutheil, 2019]. In addition, female physicians in training appear to be at a higher rate for depression which may be related to imbalances in work and household obligations [Guille,2017]. Numerous studies have demonstrated a higher prevalence of depression or emotional distress including anxiety, irritability, loneliness and stress among trainees and physicians. These conditions have been associated with adverse outcomes, including patient care errors, medical leaves, career shifts, and even suicide [Collier 2002, Craig 1968, Fahrenkopf 2008, Reuben 1985, West 2006, West 2009, Pospos 2019]. Emotional

distress not only poses health risk to the individual but has also been linked to poor-quality patient care and increased medical errors [Mata 2015, West 2009].

Studies have also shown that only a minority of physicians utilize mental health services [Nobleza, 2021]. Preventative strategies need to include recognition and management of stress and depression symptoms. Physicians in training have limited free time and unpredictable schedules limit ability to schedule appointments with mental health care providers. Artificial intelligence (AI) has been shown to comprehend language and respond with conversational and knowledgeable answers [OpenAI]. The effectiveness of the use of an AI therapist has not been evaluated in the management of mental wellness in regards to symptoms of depression and anxiety in physicians in training.

Artificial intelligence powered mental health support could provide an opportunity for mental health support that is easier to implement within the constrained work schedules of trainees. We propose a self-guided AI powered mental health support tool for physicians in training as an additional resource to address mental health management such as symptoms of depression and anxiety to promote mental health wellness in physicians in training.

## 3.0 Study Purpose and Objectives

The purpose of this pilot study is to evaluate the acceptablity of an Artificial Intelligence (AI) mental health support system as an additional resource to address mental health wellness amongst physicians in training at Cedars Sinai. The AI program is not meant to be an intervention or to replace mental health resources for the treatment of depression and anxiety diagnosis.

The primary objective is to determine if the trainees find the AI sessions through a web browser to be an acceptable and feasible wellness resource for promoting mental health wellness. A pre and post intervention survey evaluating depression symptoms with the standardized PHQ-9 questionnaire and anxiety symptoms with the standardized GAD-7 questionnaire will be conducted as a measure of mental health wellness.

The secondary objectives of this study are to:

- Evaluate the prevalence of depression and anxiety in training physicians
- Determine what work-related and home-related factors physicians in training believe impact their mental health.
- To describe the acceptance and feasibility of AI powered mental health support sessions for physicians in training. If our study shows these sessions to be efficacious and feasible in this pilot cohort, we plan to recruit other training physicians in a larger study here at Cedars Sinai.

•

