## 4.0 Study Population

Physicians in training at Cedars Sinai.

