#### 4.2 Exclusion Criteria

- Pregnancy
- Active treatment of severe and uncontrolled anxiety or depression with a health care professional
- Unwilling and or unable to participate
- Non-English speakers.

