## 4.3 Subject Identification, Recruitment, and Consent

Subjects will be initially identified in the following ways:

• The study population will be identified from the internal medicine residency and gastroenterology fellowship roster at Cedars Sinai. All subject's will be invited to participate in this study. Subjects will be recruited through an e-mail sent to the group roster and through didactic announcements.

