### 5.2 Study Design and Duration

This is a prospective pilot study with internal medicine residents and gastroenterology fellows to evaluate the role of AI mental health support tool as a wellness resource.

Participants will be invited via e-mail to participate in the study. ]The invitation e-mail will describe the study and ask that those who meet exclusion criteria do not participate in this pilot study. The e-mail will also include a file with information of the study for participants to review including how study members are blinded and the de-coding process required for participants to be contacted by our social worker should they score  $\geq$ 15 on PHQ-9 and or  $\geq$ 10 on GAD-7. Those who choose to participate will be asked email our team member who is not involved in trainee education who will send the participants a REDCap link to the consent, survey and a code to be used in the survey.

Participants will be asked to complete a set of questionnaires (Appendix B, C and D) to evaluate their mental health and factors that contribute to mental health as well as four AI powered mental health support sessions over a four-week period. This will conclude the active phase of their participations. Participants will then be sent a questionnaire at 3 months from study initiation to complete a questionnaire evaluating their mental health and if they would be interested in additional AI powered mental health support sessions.

The questionnaires will be administered before the AI sessions and at the end of the study period to evaluate for changes in mental health scores. The questionnaires will include the validated PHQ-9 for a standardized depression score and the GAD-7 for a standardized anxiety score to evaluate symptoms related to depression and anxiety. In addition, a set of questions will focus on demographics, work and home environment to evaluate factors that may contribute to mental health prior to the AI sessions and a set of questions related to the AI sessions at the end of the study period. The questionnaire will be administered via REDCap.

To maintain subject safety and confidentiality the following work-flow will be followed.

- 1. Participants who choose to participate in the study will be given a redcap link for the consent form, survey and a code via e-mail. In order to complete the consent and survey, participants will have to enter the code provided to them.

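### The prevalence objective names training physicians, but the design measures at most 20 self-selected volunteers, with some treated cases asked to stay out

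*Protocol*

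**What the plan says.** The first secondary objective in Protocol section 3.0 is "Evaluate the prevalence of depression and anxiety in training physicians". It is not limited to the people enrolled. The third objective in the same list does have a term for that group: "If our study shows these sessions to be efficacious and feasible in this pilot cohort". It goes on to mention recruiting other trainees in a later, larger study.

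The route into the data is set out elsewhere in the protocol:

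- Section 4.0 gives the population as "Physicians in training at Cedars Sinai", and section 4.3 gives the frame: "The study population will be identified from the internal medicine residency and gastroenterology fellowship roster at Cedars Sinai". Everyone on the roster is invited.
- Section 4.2 excludes "Active treatment of severe and uncontrolled anxiety or depression with a health care professional". Section 5.2 applies this through the invitation e-mail, which will "ask that those who meet exclusion criteria do not participate in this pilot study".
- Section 5.2 then makes entry an active step: "Those who choose to participate will be asked email our team member who is not involved in trainee education". Only after that step do trainees receive the link to the consent form and survey. The invitation material also explains that high scorers can be de-coded and contacted by the social worker.
- Section 6.1 states that the questionnaires are the only source of data.
- Sections 8.1 and 8.2 set the sample at 20, and at most 20.

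For context, section 2.0 cites earlier work "with an estimated 20-43% of trainee physicians experiencing depression and symptoms of depression".

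**The concern.** A prevalence is the share of a defined population that has a condition. Estimating it requires measuring that population or a sample whose selection does not depend on the condition. Here selection may depend on it in two ways.

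First, some people with the condition are asked to stay out before any score is taken. The criterion is narrow, so the effect is probably small, but it removes only cases.

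Second, the people measured are those who want AI mental health sessions enough to write in. The direction of this selection is unknown. The offer may attract trainees with symptoms, while the announced de-coding and social-worker contact may deter them.

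If the objective is followed as worded, the share of volunteers with raised scores would be reported as the prevalence in training physicians. A larger sample recruited in the same way would carry the same bias, and an analysis plan could not correct for non-participants on whom no symptom data exist.

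**Working it through.** The protocol gives no precision or power calculation for its 20 subjects, so there is no figure to reproduce. Two checks apply: precision if selection were ideal, and sensitivity to selection.

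**Inputs.** From the protocol: n = 20 (sections 8.1 and 8.2) and the background range of 20% to 43% (section 2.0). Assumed, because the protocol gives no values: a middle prevalence of 30%, the share f of cases removed by the exclusion, and the ratio v of volunteering in cases to volunteering in non-cases.

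**Precision.** Exact (Clopper-Pearson) 95% intervals for k cases out of 20:

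| k | Observed | 95% interval |
|---|---|---|
| 3 | 15% | 3.2% to 37.9% |
| 4 | 20% | 5.7% to 43.7% |
| 5 | 25% | 8.7% to 49.1% |
| 6 | 30% | 11.9% to 54.3% |
| 7 | 35% | 15.4% to 59.2% |
| 8 | 40% | 19.1% to 63.9% |
| 9 | 45% | 23.1% to 68.5% |

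For k = 4 to 8 the interval contains the whole of 20% to 43%. At k = 3 the upper limit falls below 43%, and at k = 9 the lower limit rises above 20%. So for any count from 4 to 8, even a random sample of 20 would not narrow the range already cited.

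**Selection.** With true prevalence p, the expected share among volunteers is

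p(1 − f)v / [p(1 − f)v + (1 − p)].

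With f = 0, the ratio v that moves a true value to a given observed value is the ratio of their odds:

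- 30% to 40%: (0.40/0.60) / (0.30/0.70) = 1.56
- 30% to 20%: (0.20/0.80) / (0.30/0.70) = 0.58
- 20% to 43%: (0.43/0.57) / (0.20/0.80) = 3.02

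With f = 0.10 and v between 0.5 and 2, both assumed:

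| True p | v = 0.5 | v = 1 (exclusion only) | v = 2 |
|---|---|---|---|
| 20% | 10.1% | 18.4% | 31.0% |
| 30% | 16.2% | 27.8% | 43.5% |
| 43% | 25.3% | 40.4% | 57.6% |

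For example, p = 0.30 and v = 2 gives 0.30 × 0.90 × 2 = 0.54, and 0.54 / (0.54 + 0.70) = 43.5%. The middle column shows that the exclusion alone does little. Differential volunteering could do much more, in either direction.

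**The case against.** The best defence is that the wording is loose rather than wrong. Section 3.0 speaks of recruiting other training physicians later, which makes the enrolled trainees training physicians too, and section 4.1 uses the same label for those eligible at this site. On that reading the objective already means the trainees in this pilot. The protocol also calls itself a single-site pilot throughout, sets an aim rather than reporting a prevalence, and plans no inference.

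Part of this stands. The protocol states an intention and makes no numerical claim. But the word for other trainees makes the cohort a subset of a wider class, and the objective names the class. On the narrower local reading, opt-in volunteers still do not represent the roster. If participants were meant all along, saying so costs nothing.

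Several smaller objections are fair and limit the weight. The exclusion reaches only treated, severe and uncontrolled illness, so untreated cases can enrol. Volunteer selection affects any consented survey. The values of f and v are assumptions and show that bias is possible, not that it is present. The 20-43% range concerns depression only, and the objective does not promise to narrow it. The intervals ignore the finite roster, whose size is not stated. If it were 60 to 200 (assumed), the factor √[(N − 20)/(N − 1)] would shrink half-widths only to about 0.82 to 0.95 of their size. None of this lets the design estimate the quantity the objective names.

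**Conclusion.** The concern holds. The objective asks for a population prevalence, and recruitment and eligibility allow only the share of enrolled volunteers with raised scores. The mismatch lies within the protocol itself and cannot be left to an analysis plan. The imprecision follows directly from n = 20. The size and sign of the selection bias are unknown, and the illustrations rest on assumed values of f and v and, for the middle case, an assumed 30%.

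The weight is minor to moderate. One secondary objective is affected. The primary aim of acceptability and feasibility is not, and 20 subjects is no error for that aim.

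**What to change.** Reword the objective along these lines: describe baseline PHQ-9 and GAD-7 scores, and the proportion with elevated scores, among enrolled participants. State in the same place which score defines elevated for this description. Make no statement about prevalence in training physicians. Report the number invited from the roster beside the number enrolled, so that readers can judge how selected the group is.

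The cost is one changed sentence and one count from a roster already used for recruitment. No procedure, sample size or clinical rule changes. The price is a more modest secondary aim.

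If a roster-wide prevalence is truly wanted, it needs a survey of the whole roster separate from enrolment in the sessions. For a 95% half-width of 10 points, 1.96² × p(1 − p) / 0.10² gives about 62 respondents at p = 0.20 and 95 at p = 0.43, before any finite-population correction. Reaching those numbers through the present opt-in route would not remove the selection.

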#### **Potential Benefits**

We expected little to no immediate benefit to be incurred by exposure of participants to one 20-minute session of AI powered mental health support. However, those who complete the 4 sessions over the course of the 4 weeks may experience mental health benefits. The long-term potential benefit of this investigation is evaluating the safety and feasibility of AI-powered mental health support tool over the course of 4 weeks. In doing so, the overall benefits and limitations of this approach will be better understood for future investigations and potential implementation. Furthermore, the information yielded from this investigation will inform further research and development of AI powered mental health support, which, if proven efficacious and safe, has the potential to greatly increase accessibility to high-quality mental health support to physicians in training with limited free time.

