- 2. Our social worker will be the only study members with a list of the subject's email and code.
- 3. Our social worker will review the survey responses on redcap.
- 4. If a participant survey has as a score on the PHQ9 >15 and or GAD>10, our social worker will contact the participant for evaluation and provide additional resources as needed.

5. During the sessions, XAIA will be programed to send a text message to our social worker from participants who report actionable comments such as suicidal thoughts and concerns. Our social worker will be available to receive the messages from XAIA and contact the trainee for immediate intervention and connect the trainee to additional resources as needed. In addition, a psychiatrist physician will be available for any urgent psychiatric attention.

The AI powered sessions will be administered via a web browser such as a computer, laptop, tablets or cellphone. Participants can complete the session in the privacy of their home or in a private location at work such as a call-room. Participants will be asked to complete one 20-minute session per week during the 4-week study period for a total of four sessions.

The AI program used will be the XAIA software program. XAIA was developed at Cedars Sinai. Participants will be sent an email with the link to use the XAIA software. This includes a tutorial on how to use XAIA. Typical interactions with XAIA involve a process of XAIA initially probing for topics with general inquiries "So [name], how can I help?", then asking more indepth questions about a particular topic identified by the participant, and then offering support and/or coping methods about the identified problem or topic. Once XAIA is done speaking, the participant will answer the questions and press the "done speaking" button. XAIA then processes the messages and then replies. This process repeats until the participant informs XAIA that they wish to end the session and can click the "end session" button.

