#### **Behavioral Intervention:**

This study involves a behavioral intervention. The behavioral intervention is the completion of a self-guided AI mental health support sessions by each participant. Participants will be asked to complete the session once per week for four consecutive weeks. Each session should take 20 minutes for completion. This intervention will take place at the participant's home or at Cedars in a location with access to a web browser via computer, tablet or cellphone. Those who choose to complete the session at Cedars-Sinai, may choose to use a call room dedicated for trainees. The intervention will be implemented by participants themselves.

The behavioral intervention will be implemented in the following manner:

- Participants will use the link provided by our social worker to gain access to XAIA. They
  will then follow the 2 minute tutorial provided directly by the link to use the software on
  a web browser. Participants can use a computer, laptop, tablet or cellphone with a web
  browser to access the XAIA software.
- Participants will be asked to spend 20 minutes during each session. They may choose to spend longer than 20 minutes but no more than 60 minutes.
- Participants will be asked to complete 1 session per week during the 4-week study phase.
- Participants will be asked to complete the sessions between the hours of 0700 and 2000 in order to have immediate access to our social worker and psychiatrist if needed.
- The email with link provided to access the XAIA software will include information for access to immediate mental health assistance such as a hotline provided by GME to all trainees at Cedars Sinai (Appendix E). This includes access to a mental health professional who is on call for any psychiatric emergencies.

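### Section 3.0 makes the larger study depend on this pilot showing the sessions efficacious, which its one-group before/after design cannot do and its objectives do not ask

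*Protocol*

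**What the plan says.** The last secondary objective in section 3.0 concerns describing acceptance and feasibility. It then closes with the condition for the next study: "If our study shows these sessions to be efficacious and feasible in this pilot cohort, we plan to recruit other training physicians".

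The primary objective in the same section is different. It is "to determine if the trainees find the AI sessions through a web browser to be an acceptable and feasible wellness resource".

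PHQ-9 and GAD-7 are collected alongside. The Protocol Summary (section 1.0) says the surveys "will be conducted to assess changes in mental health wellness", and section 5.2 says they are given before the sessions and "at the end of the study period to evaluate for changes in mental health scores". The schedule in section 5.1 places questionnaires at screening, Visit #4 and the 3-month follow-up, in a single set of columns.

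On who receives the sessions, the Behavioral Intervention part of section 5.3 says: "The behavioral intervention is the completion of a self-guided AI mental health support sessions by each participant".

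Section 5.2 also sets out a safety work-flow. In step 4, for a high PHQ-9 or GAD-7 score, "our social worker will contact the participant for evaluation and provide additional resources as needed". In step 5, an actionable comment during a session sends a message to the social worker, who then contacts the trainee.

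**The concern.** The sentence in section 3.0 names efficacy as something this pilot can show. The design has no means of showing it, because there is nobody in whom scores are followed without the sessions. The sentence also departs from the objectives around it, which ask only about acceptability and feasibility.

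At stake is the interpretation of the result and the stated reason for the next study. A fall in mean scores could be reported as the sessions being efficacious and put forward as the ground for wider recruitment, although time or social-worker contact alone could have produced it.

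**Working it through.** The protocol's own sample size of 20 (section 8.1) has no derivation; section 8.2 says none is required. There is therefore no figure to reproduce, and the check is mainly one of design.

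**Inputs from the protocol**
- Groups: 1, with the sessions intended for all participants (section 5.3). No control, waiting list or repeated baseline is described.
- PHQ-9/GAD-7 time points: 3, namely baseline, end of the four weeks, and 3 months (sections 5.1 and 5.3).
- Contact between measurements: triggered by score (section 5.2, step 4) or by session content (step 5).

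**Step 1: what the data contain.** For either scale at either follow-up, write

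observed mean change = A + C + T,

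where A is the effect of the AI sessions, C the effect of social-worker contact and the resources it brings, and T any change over time that would have occurred anyway. That is one observed quantity and three unknowns. For an observed change D, the case A = D with C = T = 0 and the case A = 0 with C + T = D give the same mean change. Nothing in the design tells them apart.

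**Step 2: whether C can reach the follow-up scores.**
- 4-week score: contact prompted by the baseline survey, or by a comment in an earlier session, comes before it and can affect it.
- 3-month score: the same contacts come before it. So does contact prompted by the 4-week survey, if that survey is also a trigger. Step 4 does not say which survey it means, so this last route is an inference.

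**Step 3: whether sample size matters.** In units of the SD of change, the 95% confidence interval half-width for a mean paired change is t(0.975, n−1)/√n:
- n = 20: 2.093/4.472 = 0.468
- n = 200: 1.972/14.142 = 0.139
- n = 2000: 1.961/44.721 = 0.044

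The interval narrows but stays centred on A + C + T. These figures are generic and would hold for any single-group study. They show only that more subjects would not solve the problem, and that the limit of 20 is not the fault.

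**Step 4: whether the rest of the document asks for efficacy.** The purpose and primary objective do not, and neither does any secondary objective. The Potential Benefits text treats efficacy as still open: the results "will inform further research and development of AI powered mental health support, which, if proven efficacious and safe". The assessment of risks and benefits calls the work a feasibility study. The closing sentence in section 3.0 is the only place where efficacy appears as a result of this pilot.

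**The case against.** The strongest reply is that this is one loose word. It closes a bullet about describing acceptance and feasibility. No efficacy objective, hypothesis, threshold or test appears, and the wording about changes in scores is descriptive, which one group can deliver. The only action tied to the word is recruitment to a later study; no treatment decision or participant protection depends on it. All of this stands, and it is why the point is minor. It does not make the sentence right: as written, the condition cannot be met by this design.

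A second reply is that a statistical analysis plan may deal with it. Such a plan can define estimates and tests, but it cannot supply a comparator.

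Some stronger readings are tempting and are not supported:
- A reader might infer that the pilot sets out to answer the question raised in section 2.0, "The effectiveness of the use of an AI therapist has not been evaluated in the management of mental wellness". That sentence is background, and nothing says this study will settle the matter. The link is a possible reading only.
- A reader might infer a formal go/no-go rule on efficacy. The sentence states an intention and gives no criterion.
- A reader might conclude that the score changes are no evidence at all, or that a control arm is needed. An uncontrolled change is weak and confounded evidence rather than none, and one group suffices for acceptability and feasibility.
- A reader might assume regression to the mean in the overall average. Invitations go to whole rosters and no minimum score is required for entry, so selection on score at entry does not produce it.

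**Conclusion.** Minor, but wrong as written. The condition in section 3.0 conflicts with the declared purpose and primary objective, and it claims a conclusion that a one-group before/after design with score-triggered and session-triggered contact cannot reach. The conclusion rests on the absence of any described comparator. The protocol does not use the term single-group; that is read from the sessions being intended for all participants and from the single schedule. It does not depend on an assumed SD, drift or test. The protocol gives neither the size of non-AI change nor the number likely to be contacted, so the amount of possible misattribution is not quantified.

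**What to change.** In section 3.0:
1. Replace *efficacious and feasible* with *acceptable and feasible*, so that the ground for the larger study matches the primary objective.
2. Add one sentence: *Changes in PHQ-9 and GAD-7 are descriptive and, without a comparator, cannot be attributed to the AI sessions.*

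How the changes are summarised can be left to the statistical analysis plan. The cost is one word replaced and one sentence added. Procedures, data collected, participant burden and the contact safeguard stay as they are. The one downside is that the pilot gives up efficacy as a reason for the larger study.
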